## APPENDIX 2 CLINICAL AND LABORATORY ASSESSMENTS

### Clinical Laboratory Tests

Clinical laboratory tests will be performed at the designated central laboratories at the timepoints indicated in [Section 7](#) and the Schedule of Assessments table in [Appendix 1](#). Should any laboratory parameter require urgent testing to support immediate medical care of a subject, samples should be collected for both local and central laboratory assessment. The local result may be used to manage the emergent medical situation; however, only the results from the central laboratory will be reported in the study database for analysis purposes. Urgent local laboratory testing results conflicting with the central laboratory results should be discussed between the Investigator and the study Medical Monitor.

The specific components of the clinical laboratory tests are listed below in [Table 2](#).

**Table 2: Clinical Laboratory Tests**

Panel	Tests
Clinical chemistry	Blood glucose levels, serum or plasma electrolytes (sodium, potassium, chloride, bicarbonate), calcium, blood urea nitrogen, serum creatinine, creatine kinase, GFR, uric acid, total and direct bilirubin a , ALT, AST, GGT, alkaline phosphatase, LDH, amylase, triglycerides, total cholesterol, inorganic phosphate or total phosphate, total protein, albumin, lipase, and total serum or plasma globulins
In case of elevated ALT	ALT, AST, total bilirubin, serum albumin, creatine kinase, and INR; Refer to Section 9.4 for virology and serology
Hematology	Complete blood counts: hemoglobin, hematocrit, RBC indices (MCV, MCHC), reticulocyte counts, leukocyte counts (total and differential), and platelet counts
Coagulation	Prothrombin time/INR and aPTT
Urinalysis	pH, specific gravity, protein, glucose, ketones, and occult blood
Other	AFP, HbA1c, and FSH
Pregnancy tests	For females only; a serum or plasma pregnancy test must be performed at Screening, and both serum/plasma and urine are required at Day 1; a serum, plasma, or urine pregnancy test must be performed at all subsequent visits. A positive result disqualifies the subject for study treatment
Urine drug screening	Amphetamine, barbiturates, benzodiazepines, cocaine metabolite, ethanol, opiates, and phencyclidine
Antibodies	HBcAb IgM (see Inclusion Criterion #5, Section 5.2 ), HCV, HDV, HAV IgM, HEV IgM, and HIV

Abbreviations: AFP = alpha fetoprotein; ALT = alanine aminotransferase; aPTT = activated partial thromboplastin time; AST = aspartate aminotransferase; FSH = follicle-stimulating hormone; GGT = gamma-glutamyl transpeptidase; GFR = glomerular filtration rate; HAV = hepatitis A virus; HbA1c = hemoglobin A1c; HCV = hepatitis C virus; HDV = hepatitis D virus; HEV = hepatitis E virus; IgM = immunoglobulin M; INR = International Normalized Ratio; LDH = lactate dehydrogenase; MCHC = mean corpuscular hemoglobin concentration; MCV = mean corpuscular volume; RBC = red blood cell; ULN = upper limit of normal.

a. Perform fractionated bilirubin, if total bilirubin > ULN.

### HBV Virology

To provide an assessment of the antiviral efficacy of 731 in subjects with CHB, this study will evaluate treatment effects on the following parameters:

- HBV genotyping
- HBV DNA
- HBV pgRNA

- HBsAg
- HBeAg
- HBcrAg
- HBsAb, HBeAb
- HBV sequence analysis for assessment of resistance

To ensure standardization of the virologic methodologies utilized in this study, HBV DNA-related, HBV antigen-related and HBV antibody-related virologic assessments will be conducted at a central reference laboratory. Subject serum samples for resistance-related sequencing (to be performed in the event of observing a viral breakthrough or blunted response) and HBV pgRNA testing will be shipped frozen to a designated third-party laboratory for testing. The HBV virology tests will be performed at the timepoints indicated in [Section 7](#) and the Schedule of Assessments table in [Appendix 1](#).

Additional details concerning the collection and processing of HBV virology samples are described in the Laboratory Manual.

## **Other Safety Assessments**

### 12-lead ECG:

Prior to the conduct of 12-lead ECGs, subjects should rest in a supine position for 10 minutes. ECGs should be conducted in accordance with local practice and equipment. The ECG assessment will include interpretation of the tracings (eg, rhythm, presence of arrhythmia or conduction defects, morphology, any evidence of myocardial infarction, or ST segment, T-wave, and U-wave abnormalities). The Investigator or a physician sub-investigator is responsible for reviewing and overreading the ECG interpretation, for assessing whether the ECG machine interpretation findings are accurate, appropriate, normal or abnormal, and for providing corrected interpretations as appropriate. In addition, any abnormal ECGs will be assessed for clinical significance.

Additional ECGs may be obtained if clinically indicated and will be obtained if abnormal and clinically significant or thought to be an error (eg, lead placement error, movement artifact, etc.). Any additional relevant data obtained by the Investigator during the course of this study will be recorded in the subject's source documentation. The Investigator or a physician sub-investigator will review all ECGs, evaluate the results, and sign/date the tracing or report. For any ECG abnormality that the Investigator considers clinically significant, the Investigator will:

- Repeat the ECG;
- Obtain follow-up ECG(s) if any significant abnormalities are detected after study drug administration to document resolution and as clinically indicated;
- Record as an AE any ECG abnormality that: (1) is confirmed and the Investigator considers clinically significant; (2) requires a subject to be discontinued from the study; or (3) the abnormality requires a subject to receive treatment. ([Section 8](#)).

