- Study drug administration (731, ETV and Peg-IFN $\alpha$  [as applicable])

The following assessments must be completed postdose on Day 1:

- Provide dosing diary to subjects
- Study drug dispensation (731, ETV, and Peg-IFN $\alpha$  [as applicable])
- PK samples: postdose samples for 731, Peg-IFN $\alpha$ , and ETV between 2 and 4 hours following study drug administration ([Section 7.11](#))

#### 7.4. Study Week 1

The following assessments are performed at Study Week 1:

- Symptom-directed physical examination
- Review concomitant medications
- Review AEs
- Laboratory analyses (additional details are provided in the Laboratory Manual):
  - Virology: HBV DNA, HBV pgRNA, sample for HBV sequencing and HBV nucleic acids ([Appendix 2](#))
- Review dosing diary and assess drug accountability

#### 7.5. Study Weeks 2 Through 24

The following assessments are performed at Study Weeks 2, 4, 6, 8, 12, 16, 20, and 24 (inclusive) unless otherwise indicated. Subjects who discontinue treatment before Week 24 should immediately undergo the assessments listed for the Premature Termination Visit and then continue the scheduled follow-up assessments. A visit window of  $\pm 3$  days is applied to each visit through Week 20. A visit window of -3 days is applied to Week 24 ([Appendix 1](#)).

- Liver staging (Week 24 only)
- Measure body weight (Week 24 only)
- Vital signs (temperature, heart rate, respiration rate, and blood pressure; not at Week 6)
- Complete physical examination (excluding breast and genitalia, unless indicated; Week 24 only)
- Symptom-directed physical examination (not at Week 24)
- 12-lead ECG (Weeks 12 and 24 only)
- Review concomitant medications
- Review AEs
- Laboratory analyses (additional details are provided in the Laboratory Manual):
  - Safety labs: chemistry (not at Week 6), hematology (not at Week 6), coagulation (not at Week 2 or 6), TSH (only at Weeks 12 and 24), urinalysis (not at Week 2 or 6), urine pregnancy test (not at Week 6) ([Appendix 2](#))
  - Virology: HBV DNA, HBV pgRNA, HBsAg (not at Week 2 or 6), HBeAg (not at Week 2 or 6), HBcAg (not at Week 2 or 6), HBsAb and HBeAb (Weeks 12 and 24 only), sample for HBV sequencing and HBV nucleic acids ([Appendix 2](#))

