## 7.9. Premature Termination Visit

Should a subject prematurely discontinue treatment ([Section 7.10.1](#)) or discontinue from the study ([Section 7.10](#)), a Premature Termination Visit should be scheduled. While the Investigator may include additional assessments and evaluations determined by the status of the individual subject, at the minimum, the following assessments should be performed as soon as feasibly possible:

- Measure body weight
- Vital signs (temperature, heart rate, respiration rate, and blood pressure)
- Complete physical examination (excluding breast and genitalia unless indicated)
- 12-lead ECG
- Review concomitant medications
- Review AEs
- Laboratory analyses (additional details are provided in the Laboratory Manual):
  - Safety labs: chemistry, hematology, coagulation, urinalysis, urine drug test, urine pregnancy test ([Appendix 2](#))
  - Virology: HBV DNA, HBV pgRNA, HBsAg, HBeAg, HBcrAg, HBsAb, and HBeAb, sample for HBV sequencing and HBV nucleic acids ([Appendix 2](#))
  - PK samples: samples for 731 and Peg-IFN $\alpha$  (if appropriate), and ETV ([Section 7.11](#))
- Review dosing diary and assess drug accountability (if applicable)

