## 1.3. Sample Size and Power

Approximately 60 eligible male or female subjects between the ages of 18 and 65 years with HBeAg positive cHBV will be enrolled in the study. Subjects will be randomized to receive 1 of the following 3 treatments, VBR+ETV, ETV+Peg-IFN $\alpha$ , or VBR+ETV+Peg-IFN $\alpha$  in a 1:1:1 ratio.

This is a proof-of-concept study. The sample size is similar to that previously utilized for this type of study and is not based upon statistical considerations.

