**Table 3-5 On-Treatment Analysis Visit Windows for ECG**

Nominal Visit	On-Treatment Nominal Study Day	Visit Window Study Day	
		Lower Limit	Upper Limit
Day 1	1	(none)	1
Week 12	84	2	126
Week 24	168	127	252
Week 48	336	253	≥336

The analysis windows for Follow-up Phase study assessments of efficacy (except HBsAb and HBeAb), vital signs, and laboratory assessments (chemistry, hematology, coagulation and urinalysis) are provided in Table 3-6.

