### 3.6.5. Selection of Data in the Event of Multiple Records in an Analysis Visit Window

Depending on the statistical analysis method, single values may be required for each analysis window. If a single value is needed, but multiple valid, nonmissing measurements exist in an analysis window, records will be chosen based on the following rules:

- For Baseline, the last nonmissing value on or prior to the first dose date of study drug will be selected, unless specified differently. If there are multiple records with the same time or no time recorded on the same day, the record with the lowest accession number will be selected as the baseline value.
- For postbaseline values:
  - The record closest to the nominal day for that visit will be selected with the exception of virology parameters in which the latest record will be selected.
  - If there are 2 records that are equidistant from the nominal day, the later record will be selected.
  - If there is more than 1 record on the selected day with the same time, the retest record will be selected. If there is no clear indication for which record is the retest record, then the record with the lowest accession number will be selected.

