## 7.5. **Electrocardiogram Results**

A shift table of the investigators' assessment of ECG results at each visit compared with baseline values will be presented by treatment group using the following categories:

- normal
- abnormal (not clinically significant)
- abnormal (clinically significant)
- missing/not done

The number and percentage of subjects in each cross-classification group of the shift table will be presented. Subjects with a missing value at Baseline or postbaseline will not be included in the denominator for percentage calculation.

A by-subject listing for ECG assessment results will be provided by subject ID number and visit in chronological order.

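### The SAP's by-visit ECG shift table drops most between-visit ECGs and some premature-termination ECGs from its on-treatment rows, and no worst-postbaseline summary picks them up

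*Combined protocol and SAP*

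**What the plan says.** **Protocol.** On-treatment ECGs are scheduled at Weeks 12, 24 and 48, with one at Week 60 in follow-up (Sections 7.5 to 7.7). Week 12 may fall 3 days either side of target. For the next ECG visit, "A visit window of -3 days is applied to Week 24", and Week 48 has the same one-sided window. Appendix 2 requires a clinically significant ECG to be repeated, and the investigator is to "Obtain follow-up ECG(s) if any significant abnormalities are detected after study drug administration to document resolution and as clinically indicated". Section 7.9 begins "Should a subject prematurely discontinue treatment", extends to leaving the study, and includes an ECG among the minimum assessments.

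**SAP 7.5.** "A shift table of the investigators' assessment of ECG results at each visit compared with baseline values will be presented by treatment group". The categories are normal, abnormal not clinically significant, abnormal clinically significant, and missing or not done. A by-subject listing accompanies the table. Section 7.6 adds no further safety measures because of the early termination.

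**SAP Table 3-5**, "On-Treatment Analysis Visit Windows for ECG":

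| Row | Nominal day | Window (study days) |
|---|---|---|
| Week 12 | 84 | 2-126 |
| Week 24 | 168 | 127-252 |
| Week 48 | 336 | 253 onward |

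**SAP 3.6.5.** Where one value per window is needed, "The record closest to the nominal day for that visit will be selected", and the later record wins a tie. Only virology parameters are exempt. Section 7.5 does not cite this rule for ECGs, but a subject can occupy only one shift cell per visit, so the rule applies.

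**SAP 3.6.2 and 3.6.4.** Premature-termination data serve as Follow-Up Baseline, and the follow-up phase is labelled off treatment.

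**The concern.** The protocol asks for extra ECGs when something looks wrong or when treatment stops. The only by-arm table of ECG categories has room for one ECG per window and chooses it by date, not by result or by why it was taken. The SAP handles other safety data differently: laboratory abnormalities (7.2.1.2) and adverse-event severity (7.1.6) are both summarised by the most severe grade. ECGs have no such row.

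Two kinds of information are at stake. One is a shift to abnormal but not clinically significant, which is a category of the table but need not be recorded as an adverse event. The other is Group 3's time on VBR. That group starts VBR at Week 24, and its next scheduled ECG is at Week 48. The sponsor ended treatment early in July 2022 (SAP Section 1), so premature-termination ECGs are foreseeable, although the documents give no count.

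**Working it through.** **1. Window limits.** These are midpoints of adjacent nominal days: (84 + 168)/2 = 126 and (168 + 336)/2 = 252, which matches Table 3-5. The windows span 125, 126 and at least 84 days.

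**2. ECGs between visits.** With all three scheduled ECGs done, Days 2-336 leave 335 - 3 = 332 possible days for an unscheduled ECG.
- Visits on Days 84, 168 and 336: it is selected on 0 of 332 days.
- Visits on Days 87, 168 and 336: 5 of 332 (Days 82-86).
- Visits on Days 81, 165 and 333: 15 of 332 (4.5%), namely Days 82-87, 166-171 and 334-336. SAP 3.6.2 ends the on-treatment phase at the Week 48 visit. If that is enforced, Days 334-336 drop out and the count is 12 of 332 (3.6%).

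Example: an abnormal ECG on Day 40 is 44 days from Day 84 and loses to the Week 12 ECG.

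**3. Premature-termination (PT) ECGs.** These can fall on Days 2-335, which is 334 days. Assume any scheduled ECG due before the PT day was done. The PT ECG is displaced if it lies further from the nominal day than the scheduled ECG in the same window.

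| Week 12 / Week 24 ECG on Days | PT days displaced | Total | Share of 334 |
|---|---|---|---|
| 84 / 168 | 85-126 (42), 169-252 (84) | 126 | 37.7% |
| 85 / 169 | 86-126 (41), 170-252 (83) | 124 | 37.1% |
| 87 / 168 | 88-126 (39), 169-252 (84) | 123 | 36.8% |
| 81 / 165 | 88-126 (39), 172-252 (81) | 120 | 35.9% |

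In the first row the PT ECG is the selected record on Days 2-84, 127-168 and 253-335: 83 + 42 + 83 = 208 days (62.3%).

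**4. Group 3.** VBR starts at Week 24. If the Week 24 ECG is on Day 168 and the subject stops on Days 169-252, the PT ECG can be the only protocol-required ECG on VBR. The Week 24 row keeps the Day 168 ECG, so the on-treatment rows show none of that subject's VBR exposure. From Day 253 the PT ECG enters the Week 48 row.

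**5. Abnormal ECG at a scheduled visit.** Let the visit be k days before nominal and the follow-up ECG j days after the visit. The follow-up is |j - k| days from nominal, so it replaces the abnormal record when |j - k| <= k, that is, j <= 2k.
- k = 1, 2 or 3: follow-up within 2, 4 or 6 days.
- Visit on or after nominal: only a same-day repeat replaces it.
- Lag of 7 days or more: never.

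Example: abnormal on Day 165 and normal on Day 171 are both 3 days from Day 168, so the later one is kept. If sites count Week 24 as 168 days after Day 1 (Study Day 169), visits fall on Days 166-169, k is at most 2, and the longest replacing lag is 4 days. At Week 48, the phase boundary in step 2 would send a later-day ECG to follow-up, leaving only the same-day repeat.

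**6. The Follow-Up Baseline route.** SAP 3.6.3 makes follow-up Day 1 the day after the PT visit and defines follow-up day as assessment date minus that day plus 1. For a PT visit on day D this gives D - (D + 1) + 1 = 0. Table 3-7 ends Follow-Up Baseline at -1 and starts the next window at 1, so Day 0 has no row. The predose formula in 3.6.3, without the plus 1, would give -1, but it is stated only for the on-treatment phases.

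**The case against.** Clinically important findings already have a by-arm route. A confirmed, clinically significant ECG abnormality, or one that leads to study discontinuation or needs treatment, is recorded as an adverse event (protocol Appendix 2), and SAP 7.1.6 tabulates those by arm. ECG results are also listed by subject. The primary endpoint names adverse events, discontinuation and laboratory results, not ECGs. The study has about 60 subjects and no formal inference, and the SAP was deliberately shortened. All of this stands and limits how much the point matters. It does not cover abnormalities that never become adverse events, which would survive only in an unsummarised listing.

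Three stronger readings are tempting, and the documents do not support them.
- *Wide windows let resolution ECGs routinely overwrite abnormal ones.* At a scheduled visit, replacement depends on an early visit and a short lag, or a same-day repeat. Window width matters for between-visit and PT ECGs.
- *PT ECGs never enter the table.* They are the selected on-treatment record on about 62% of possible days and are otherwise assigned to Follow-Up Baseline. The SAP does not say whether that row appears in the shift table.
- *The rule favours normal results.* It ignores the result, so a later abnormal ECG can equally replace a normal one. Any tilt towards normal arises only because follow-up ECGs are prompted by abnormal ones.

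Nor is a PT ECG normally a Group 3 subject's only ECG after starting VBR: early stoppers continue follow-up, which includes the Week 60 ECG. It can be the only required one while on VBR.

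**Conclusion.** The point holds within limits. When scheduled ECGs are done, the on-treatment rows omit between-visit ECGs on at least 95% of possible days. They omit PT ECGs on roughly Days 85-126 and 169-252, or 36-38% of possible days. These are shares of calendar days: they treat each day as equally likely and assume the preceding scheduled ECG was done, because the documents give no distribution of PT or unscheduled visits. They are not estimates of the share of ECGs lost. The displacement itself follows from the rules and does not depend on that assumption.

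The loss is confined to the shift table. It falls mainly on abnormalities not recorded as adverse events and on Group 3's exposure to VBR. The Follow-Up Baseline route does not repair it as written, because that phase is labelled off treatment and the PT visit falls on an uncovered day. The change is worth making, but the gap does not hide confirmed significant ECGs from safety reporting.

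**What to change.** 1. In SAP 7.5, add a shift from Baseline to the worst postbaseline category (clinically significant, then not clinically significant, then normal). Use all scheduled, unscheduled and PT ECGs, separately for Day 1 to the Week 24 visit and for Week 24 to the end of VBR. State that the second period includes the PT ECG. Where a repeat does not confirm a finding, the repeat supersedes the original.
2. In the by-visit table, show PT ECGs as their own row.
3. In SAP 3.6.3 or Table 3-7, correct the day numbering so that the PT visit falls in Follow-Up Baseline.

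The cost is SAP wording and one extra table from data already collected, with no new procedures. SAP Section 1 allows changes made after finalisation to be documented in the Synoptic CSR. The downside is slightly higher abnormality counts, because subjects with more ECGs have more chances of an abnormal one; a footnote giving the number of ECGs per subject in each group would let readers allow for that.

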### Complete Physical Examination:

Complete physical examinations will be performed by the Investigator or qualified sub-investigator at the time points indicated in the Study Procedures section ([Section 7](#), [Appendix 1](#)). The complete physical examination will consist of the following body systems: head, eyes, ears, nose, and throat; cardiovascular; respiratory; gastrointestinal; dermatologic; musculoskeletal; nervous; extremities; and

lymph nodes. Additional body systems may be evaluated at the Investigator's discretion. Examination of the breast and genitalia are not required unless clinically indicated.

Additional symptom-directed physical examinations will be performed at the time points indicated in the Study Procedures section ([Section 7](#); [Appendix 1](#)). Additional symptom-directed or complete physical examinations made be performed at the Investigator's discretion throughout the course of the study. If the subject reports feeling unwell or has ongoing AEs, the Investigator or qualified sub-investigator will examine the appropriate body system(s).

## APPENDIX 3 TOXICITY GRADING SCALE FOR ADVERSE EVENTS AND LABORATORY ABNORMALITIES

Adapted from the US National Institutes of Health (DAIDS) Table for Grading Severity of Adult Adverse Experiences (July 2017).

### MAJOR CLINICAL CONDITIONS

Cardiovascular				
Parameter	Grade 1 Mild	Grade 2 Moderate	Grade 3 Severe	Grade 4 Potentially Life-threatening
Arrhythmia (by ECG or physical examination) Specify type, if applicable	No symptoms AND no intervention indicated	No symptoms AND non-urgent intervention indicated	Non-life-threatening symptoms AND Non-urgent intervention indicated	Life-threatening arrhythmia OR urgent intervention indicated
Blood Pressure Abnormalities  Hypertension (with the lowest reading taken after repeat testing during a visit) ≥18 years of age	140 to <160 mmHg systolic OR 90 to <100 mmHg diastolic	≥160 to <180 mmHg systolic OR ≥100 to <110 mmHg diastolic	≥180 mmHg systolic OR ≥110 mmHg diastolic	Life-threatening consequences in a subject not previously diagnosed with hypertension (eg, malignant hypertension) OR hospitalization indicated
Hypotension	No symptoms	Symptoms corrected with oral fluid replacement	Symptoms AND IV fluids indicated	Shock requiring use of vasopressors or mechanical assistance to maintain blood pressure
Cardiac Ischemia or Infarction Report only one	NA	NA	New symptoms with ischemia (stable angina) OR New testing consistent with ischemia	Unstable angina OR Acute myocardial infarction
Heart Failure	No symptoms AND Laboratory or cardiac imaging abnormalities	Symptoms with mild to moderate activity or exertion	Symptoms at rest or with minimal activity or exertion (eg, hypoxemia) OR Intervention indicated (eg, oxygen)	Life-threatening consequences OR Urgent intervention indicated (eg, vasoactive medications, ventricular assist device, heart transplant)
Hemorrhage (with significant acute blood loss)	NA	Symptoms AND No transfusion indicated	Symptoms AND Transfusion of ≤2 units packed RBCs indicated	Life-threatening hypotension OR Transfusion of >2 units packed RBCs indicated

Cardiovascular				
Parameter	Grade 1 Mild	Grade 2 Moderate	Grade 3 Severe	Grade 4 Potentially Life-threatening
Prolonged PR Interval or AV Block Report only one ≥16 years of age	PR interval 0.21 to <0.25 seconds	PR interval $\geq 0.25$ seconds OR Type I 2nd degree AV block	Type II 2nd degree AV block OR Ventricular pause $\geq 3.0$ seconds	Complete AV block
Prolonged QTc Interval a	0.45 to 0.47 seconds	>0.47 to 0.50 seconds	>0.50 seconds OR $\geq 0.06$ seconds above Baseline	Life-threatening consequences (eg, Torsade de pointes, other associated serious ventricular dysrhythmia)
Thrombosis or Embolism Report only one	NA	Symptoms AND No intervention indicated	Symptoms AND Intervention indicated	Life-threatening embolic event (eg, pulmonary embolism, thrombus)

Abbreviations: AV = atrioventricular; ECG = electrocardiogram; IV = intravenous; NA = not applicable; QTc = corrected QT interval; RBC = red blood cell.

a. As per Bazett's formula.

Dermatologic				
Parameter	Grade 1 Mild	Grade 2 Moderate	Grade 3 Severe	Grade 4 Potentially Life-threatening
Alopecia (scalp only)	Detectable by study subject, caregiver, or physician AND Causing no or minimal interference with usual social and functional activities	Obvious on visual inspection AND Causing greater than minimal interference with usual social and functional activities	NA	NA
Bruising	Localized to 1 area	Localized to more than 1 area	Generalized	NA
Cellulitis	NA	Non-parenteral treatment indicated (eg, oral antibiotics, antifungals, antivirals)	IV treatment indicated (eg, IV antibiotics, antifungals, antivirals)	Life-threatening consequences (eg, sepsis, tissue necrosis)
Hyperpigmentation	Slight or localized causing no or minimal interference with usual social and functional activities	Marked or generalized causing greater than minimal interference with usual social and functional activities	NA	NA
Hypopigmentation	Slight or localized causing no or minimal interference with usual social and functional activities	Marked or generalized causing greater than minimal interference with usual social and functional activities	NA	NA
Petechiae	Localized to 1 area	Localized to more than 1 area	Generalized	NA
Pruritusb (without skin lesions)	Itching causing no or minimal interference with usual social and functional activities	Itching causing greater than minimal interference with usual social and functional activities	Itching causing inability to perform usual social and functional activities	NA
Rash Specify type, if applicable	Localized rash	Diffuse rash OR Target lesions	Diffuse rash AND Vesicles or limited number of bullae or superficial ulcerations of mucous membrane limited to 1 site	Extensive or generalized bullous lesions OR Ulceration of mucous membrane involving 2 or more distinct mucosal sites OR Stevens-Johnson syndrome OR Toxic epidermal necrolysis

Abbreviations: IV = intravenous; NA = not applicable.

b. For pruritus associated with injections or infusions, see the Site Reactions to Injections and Infusions section.

Endocrine and Metabolic				
Parameter	Grade 1 Mild	Grade 2 Moderate	Grade 3 Severe	Grade 4 Potentially Life-Threatening
Diabetes Mellitus	Controlled without medication	Controlled with medication OR Modification of current medication regimen	Uncontrolled despite treatment modification OR Hospitalization for immediate glucose control indicated	Life-threatening consequences (eg, ketoacidosis, hyperosmolar non-ketotic coma, end organ failure)
Gynecomastia	Detectable by study subject, caregiver, or physician AND Causing no or minimal interference with usual social and functional activities	Obvious on visual inspection AND Causing pain with greater than minimal interference with usual social and functional activities	Disfiguring changes AND Symptoms requiring intervention or causing inability to perform usual social and functional activities	NA
Hyperthyroidism	No symptoms AND Abnormal laboratory value	Symptoms causing greater than minimal interference with usual social and functional activities OR Thyroid suppression therapy indicated	Symptoms causing inability to perform usual social and functional activities OR Uncontrolled despite treatment modification	Life-threatening consequences (eg, thyroid storm)
Hypothyroidism	No symptoms AND Abnormal laboratory value	Symptoms causing greater than minimal interference with usual social and functional activities OR Thyroid replacement therapy indicated	Symptoms causing inability to perform usual social and functional activities OR Uncontrolled despite treatment modification	Life-threatening consequences (eg, myxedema coma)
Lipoatrophyc	Detectable by study subject, caregiver, or physician AND Causing no or minimal interference with usual social and functional activities	Obvious on visual inspection AND Causing greater than minimal interference with usual social and functional activities	Disfiguring changes	NA
Lipohypertrophyd	Detectable by study subject, caregiver, or physician AND Causing no or minimal interference with usual social and functional activities	Obvious on visual inspection AND Causing greater than minimal interference with usual social and functional activities	Disfiguring changes	NA

Abbreviation: NA = not applicable.

c. Definition: A disorder characterized by fat loss in the face, extremities, and buttocks.

d. Definition: A disorder characterized by abnormal fat accumulation on the back of the neck, breasts, and abdomen.

Gastrointestinal				
Parameter	Grade 1 Mild	Grade 2 Moderate	Grade 3 Severe	Grade 4 Potentially Life-threatening
Anorexia	Loss of appetite without decreased oral intake	Loss of appetite associated with decreased oral intake without significant weight loss	Loss of appetite associated with significant weight loss	Life-threatening consequences OR Aggressive intervention indicated (eg, tube feeding, total parenteral nutrition)
Ascites	No symptoms	Symptoms AND Intervention indicated (eg, diuretics, therapeutic paracentesis)	Symptoms recur or persist despite intervention	Life-threatening consequences
Bloating or Distension Report only one	Symptoms causing no or minimal interference with usual social and functional activities	Symptoms causing greater than minimal interference with usual social and functional activities	Symptoms causing inability to perform usual social and functional activities	NA
Cholecystitis	NA	Symptoms AND Medical intervention indicated	Radiologic, endoscopic, or operative intervention indicated	Life-threatening consequences (eg, sepsis, perforation)
Constipation	NA	Persistent constipation requiring regular use of dietary modifications, laxatives, or enemas	Obstipation with manual evacuation indicated	Life-threatening consequences (eg, obstruction)
Diarrhea ≥1 year of age	Transient or intermittent episodes of unformed stools OR Increase of $\leq 3$ stools over Baseline per 24-hour period	Persistent episodes of unformed to watery stools OR Increase of 4 to 6 stools over Baseline per 24-hour period	Increase of $\geq 7$ stools per 24-hour period OR IV fluid replacement indicated	Life-threatening consequences (eg, hypotensive shock)
Dysphagia or Odynophagia Report only 1 and specify location	Symptoms but able to eat usual diet	Symptoms causing altered dietary intake with no intervention indicated	Symptoms causing severely altered dietary intake with intervention indicated	Life-threatening reduction in oral intake
Gastrointestinal Bleeding	Not requiring intervention other than iron supplement	Endoscopic intervention indicated	Transfusion indicated	Life-threatening consequences (eg, hypotensive shock)
Mucositis or Stomatitis Report only 1 and specify location	Mucosal erythema	Patchy pseudomembranes or ulcerations	Confluent pseudomembranes or ulcerations OR Mucosal bleeding with minor trauma	Life-threatening consequences (eg, aspiration, choking) OR Tissue necrosis OR Diffuse spontaneous mucosal bleeding
Nausea	Transient (<24 hours) or intermittent AND No or minimal interference with oral intake	Persistent nausea resulting in decreased oral intake for 24 to 48 hours	Persistent nausea resulting in minimal oral intake for $>48$ hours OR Rehydration indicated (eg, IV fluids)	Life-threatening consequences (eg, hypotensive shock)
Pancreatitis	NA	Symptoms with hospitalization not indicated	Symptoms with hospitalization indicated	Life-threatening consequences (eg, circulatory failure, hemorrhage, sepsis)
Perforation (colon or rectum)	NA	NA	Intervention indicated	Life-threatening consequences

Gastrointestinal				
Parameter	Grade 1 Mild	Grade 2 Moderate	Grade 3 Severe	Grade 4 Potentially Life-threatening
Proctitis	Rectal discomfort with no intervention indicated	Symptoms causing greater than minimal interference with usual social and functional activities OR Medical intervention indicated	Symptoms causing inability to perform usual social and functional activities OR Operative intervention indicated	Life-threatening consequences (eg, perforation)
Rectal Discharge	Visible discharge	Discharge requiring the use of pads	NA	NA
Vomiting	Transient or intermittent AND No or minimal interference with oral intake	Frequent episodes with no or mild dehydration	Persistent vomiting resulting in orthostatic hypotension OR Aggressive rehydration indicated (eg, IV fluids)	Life-threatening consequences (eg, hypotensive shock)

Abbreviations: IV = intravenous; NA = not applicable.

Musculoskeletal				
Parameter	Grade 1 Mild	Grade 2 Moderate	Grade 3 Severe	Grade 4 Potentially Life-threatening
Arthralgia	Joint pain causing no or minimal interference with usual social and functional activities	Joint pain causing greater than minimal interference with usual social and functional activities	Joint pain causing inability to perform usual social and functional activities	Disabling joint pain causing inability to perform basic self-care functions
Arthritis	Stiffness or joint swelling causing no or minimal interference with usual social and functional activities	Stiffness or joint swelling causing greater than minimal interference with usual social and functional activities	Stiffness or joint swelling causing inability to perform usual social and functional activities	Disabling joint stiffness or swelling causing inability to perform basic self-care functions
Myalgia (generalized)	Muscle pain causing no or minimal interference with usual social and functional activities	Muscle pain causing greater than minimal interference with usual social and functional activities	Muscle pain causing inability to perform usual social and functional activities	Disabling muscle pain causing inability to perform basic self-care functions
Osteonecrosis	NA	No symptoms but with radiographic findings AND No operative intervention indicated	Bone pain with radiographic findings OR Operative intervention indicated	Disabling bone pain with radiographic findings causing inability to perform basic self-care functions
Osteopenia e ≥30 years of age	BMD t-score -2.5 to -1	NA	NA	NA
<30 years of age	BMD z-score -2 to -1	NA	NA	NA
Osteoporosis e ≥30 years of age	NA	BMD t-score <-2.5	Pathologic fracture (eg, compression fracture causing loss of vertebral height)	Pathologic fracture causing life-threatening consequences
<30 years of age	NA	BMD z-score <-2	Pathologic fracture (eg, compression fracture causing loss of vertebral height)	Pathologic fracture causing life-threatening consequences

Abbreviations: BMD = bone mineral density; NA = not applicable; WHO = World Health Organization.

e. Bone mineral density t and z scores can be found in [WHO 2007](#).

Neurologic				
Parameter	Grade 1 Mild	Grade 2 Moderate	Grade 3 Severe	Grade 4 Potentially Life-threatening
Acute CNS Ischemia	NA	NA	Transient ischemic attack	Cerebral vascular accident (eg, stroke with neurological deficit)
Altered Mental Status (for Dementia, see Cognitive, Behavioral, or Attentional Disturbance below)	Changes causing no or minimal interference with usual social and functional activities	Mild lethargy or somnolence causing greater than minimal interference with usual social and functional activities	Confusion, memory impairment, lethargy, or somnolence causing inability to perform usual social and functional activities	Delirium OR Obtundation OR Coma
Ataxia	Symptoms causing no or minimal interference with usual social and functional activities OR No symptoms with ataxia detected on examination	Symptoms causing greater than minimal interference with usual social and functional activities	Symptoms causing inability to perform usual social and functional activities	Disabling symptoms causing inability to perform basic self-care functions
Cognitive, Behavioral, or Attentional Disturbance (includes dementia and attention deficit disorder) Specify type, if applicable	Disability causing no or minimal interference with usual social and functional activities OR Specialized resources not indicated	Disability causing greater than minimal interference with usual social and functional activities OR Specialized resources on part-time basis indicated	Disability causing inability to perform usual social and functional activities OR Specialized resources on a full-time basis indicated	Disability causing inability to perform basic self-care functions OR Institutionalization indicated
Headache	Symptoms causing no or minimal interference with usual social and functional activities	Symptoms causing greater than minimal interference with usual social and functional activities	Symptoms causing inability to perform usual social and functional activities	Symptoms causing inability to perform basic self-care functions OR Hospitalization indicated OR Headache with significant impairment of alertness or other neurologic function
